Title

Conservative versus Interventional Management of Postsurgical CSF
Pseudomeningocele: A Randomized Controlled Trial

NCT number

Not yet assigned

Unique protocol ID

108/20-55/2025

Date

22th May 2026

1. Background and Rationale

Background:

Postsurgical pseudomeningocele formation is a relatively common complication after intracranial surgery, often associated with fluid collection at the surgical site. Management approaches vary, with options including conservative treatment or interventional strategies such as revision surgery, insertion of lumbar drainage, or simple wound puncture. Current evidence on the most effective treatment is limited, and there is a need for randomized controlled trials to evaluate the outcomes of these approaches.

Rationale:

This trial aims to determine whether an interventional approach offers superior outcomes compared to conservative management in terms of pseudomeningocele absorption and overall patient recovery.

2. Objectives and Hypotheses

Primary Objective:

1. New onset of wound CSF leakage necessitating revision surgery

Secondary Objectives:

1. To compare the infection rate between the two treatment groups.
2. To assess functional recovery using the Glasgow Outcome Scale–Extended (GOSE) at 1 year post-surgery.
3. Absorption of pseudomeningocele at 4 months and 1 year post-surgery assessed by CT or MRI
4. Persistence of headache after the surgery – Pain Scale 0-10 (VAS)

Null Hypothesis:

There is no significant difference in the rate of CSF leakage and pseudomeningocele absorption at 4 months and 1 year, as measured by CT or MRI, between patients treated with conservative management and those undergoing interventional procedures (revision surgery, lumbar drainage, or simple puncture). Additionally, there is no significant difference in secondary outcomes, such as infection rates and functional recovery (measured by the Glasgow Outcome Scale–Extended), between the two groups.

3. Study Design

This study is a **parallel-group, randomized controlled trial** with two arms:

- **Interventional Group:** Patients undergoing local treatment - lumbar drainage insertion, simple wound puncture, fibrin glue or any combination.
- **Conservative Group:** Patients managed without surgical procedures, except for skin sutures.

Patients will be followed for a total of 1 year with CT or MRI assessments at 4 months and 1 year post-surgery.

4. Participants / Population

Inclusion Criteria:

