- Patients aged 18-80 years who have developed a pseudomeningocele following elective intracranial surgery.
- Diagnosed fluctuation during clinical examination after the surgery, Pseudomeningocele Palpation Scale (PPS), II-IV

I No or minimal fluctuation; underlying bone is clearly palpable with light palpation.

II Definite fluctuation; underlying bone or muscle is palpable with moderate pressure.

III Marked fluctuation; underlying structures are palpable only with firm pressure.

IV Tense lesion; painful and/or erythematous; underlying structures are not palpable even with firm pressure.

Light palpation: minimal pressure without causing discomfort

Moderate pressure: increased pressure causing awareness but no pain

Firm pressure: strong pressure causing discomfort or mild pain

- Willing and able to give informed consent.
- No prior history of previous cranial or spinal surgical intervention.

Exclusion Criteria:

- Patients with pseudomeningocele due to emergency or trauma-related surgeries.
- Known or suspected infection at the pseudomeningocele site at the time of recruitment.
- Severe comorbid conditions preventing participation (e.g., terminal illness, severe organ failure).
- Patients with conditions that require urgent surgical intervention not related to pseudomeningocele management.

5. Interventions

Interventional Arm:

- Patients will undergo one of the following procedures based on clinical judgment:
 1. **Revision surgery:** Surgical intervention to drain the pseudomeningocele and ensure proper wound closure.
 2. **Lumbar drainage insertion:** Placement of a lumbar drain to facilitate cerebrospinal fluid (CSF) diversion.
 3. **Simple puncture:** Needle aspiration of the pseudomeningocele under sterile conditions.

Conservative Arm:

- Patients will receive conservative management, with no surgical procedures other than the application of skin sutures if required. Monitoring and wound care will be provided.
-

6. Outcomes

Primary Outcome:

- **New onset of wound CSF leakage or tension pseudomeningocele necessitating revision surgery**

Secondary Outcomes:

- **Infection rate:**
Incidence of infection related to the pseudomeningocele or any interventions, including signs of local infection, meningitis, or systemic sepsis, within 1 year.
 - **Functional recovery (GOSE):**

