The Glasgow Outcome Scale–Extended (GOSE) will be assessed at 1 year post-surgery to evaluate functional outcomes and quality of life. GOSE scores range from 1 (death) to 8 (upper good recovery).
 - **Pseudomeningocele absorption on CT or MRI:**
The primary outcome is the resolution or reduction of the pseudomeningocele, assessed through CT or MRI at **4 months** and **1 year** post-surgery. Scans will be reviewed by blinded radiologists, and pseudomeningocele size will be measured and recorded.
 - **Visual Analogue Scale**
-

7. Randomization and Blinding

Randomization:

Participants will be randomized in a 1:1 ratio to the interventional or conservative treatment arms using a computer-generated randomization sequence. Randomization will be stratified by age and body mass index.

Blinding:

Due to the nature of the interventions, patients and surgical teams cannot be blinded to group allocation. However, the radiologists interpreting the CT or MRIs and the independent data assessors evaluating outcomes will be blinded to the treatment arm.

8. Sample Size Calculation

A sample size of **60 patients** (30 per group) will be required to detect a clinically significant difference in pseudomeningocele absorption between the two groups, with a power of 80% and an alpha of 0.05.

9. Statistical Analysis

- **Primary outcome:**
The proportion of patients requiring revision surgery for CSF leakage or tension pseudomeningocele at 4 months and 1 year will be compared between the two groups using a chi-square test. Time-to-absorption analyses will be conducted using Kaplan-Meier survival curves and log-rank tests.
 - **Secondary outcomes:**
Infection rates will be compared using Fisher's exact test, and GOSE scores will be analyzed using a Mann-Whitney U test to assess differences in functional recovery between groups.
 - **Multivariate analysis:**
Multivariate logistic regression will be used to adjust for potential confounders, such as baseline health status, age, and type of initial surgery.
-

10. Ethical Considerations

The study will be conducted following the principles of the Declaration of Helsinki. Informed consent will be obtained from all participants before enrollment. The study protocol has been approved by the institutional review board (IRB). The risks associated with interventional approaches (e.g., infection, procedural complications) will be disclosed to patients during the consent process.

11. Follow-up and Monitoring

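### The objective asks for absorption at 4 months and at 1 year, but Section 9 names only a time-to-absorption analysis, which under standard coding estimates *ever absorbed* at 1 year

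*Protocol*

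**What the plan says.** - **Objective (Protocol, Section 2, third secondary objective):** "Absorption of pseudomeningocele at 4 months and 1 year post-surgery assessed by CT or MRI". The null hypothesis in the same section likewise refers to no difference in absorption at those two times.
- **Schedule (Section 3):** "Patients will be followed for a total of 1 year with CT or MRI assessments at 4 months and 1 year post-surgery". No other imaging times are given.
- **Outcome (Section 6, within the secondary outcomes):** "The primary outcome is the resolution or reduction of the pseudomeningocele". The text continues: "Scans will be reviewed by blinded radiologists, and pseudomeningocele size will be measured and recorded". It gives no threshold for reduction, and no rule on whether the first absorbed scan or sustained absorption is meant.
- **Analysis (Section 9, under the primary outcome):** "Time-to-absorption analyses will be conducted using Kaplan-Meier survival curves and log-rank tests". The chi-square test there is for revision surgery, Fisher's exact test is for infection and the Mann-Whitney test is for GOSE. The logistic regression names no outcome.

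**The concern.** The objective is about status: is the collection absorbed at 4 months, and is it absorbed at 1 year? The named analysis is about first occurrence. The two give the same 1-year answer only if no patient scored absorbed at 4 months has lost that status by 1 year.

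In a standard Kaplan-Meier or log-rank analysis a patient leaves the risk set at the event. With only two scans, a patient scored absorbed at 4 months adds nothing from the 1-year scan, although that scan is taken and read blind. Because reduction alone can count as absorption, some patients may have an event at 4 months while fluid remains. The coarse timing of the scans is a separate matter: an interval-censored analysis of first absorption would have the same property.

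At stake is the 1-year result for the endpoint on which Section 8 bases the sample size. If loss of absorption were commoner in one arm, a temporary difference could be read as a lasting one, or a lasting one could be understated.

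**Working it through.** **Stated figure.** The only number tied to absorption is 60 patients, 30 per group (Section 8). It can be neither reproduced nor refuted, because no absorption rates are given. As a two-sided comparison of proportions without continuity correction it fits differences of about 35 points (20% v 55% needs 29 per arm; 30% v 65% needs 31). It supplies no rates for the check below.

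**Notation.** All three inputs are assumptions, as none is in the documents:
- p4: proportion absorbed at 4 months
- c: proportion of the rest who are newly absorbed by 1 year
- r: proportion of those absorbed at 4 months who no longer meet the definition at 1 year

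**Formulas.**
- First-event (Kaplan-Meier) value at 1 year = p4 + (1 − p4)c
- Status at 1 year = p4(1 − r) + (1 − p4)c
- Overstatement = p4 × r, which does not depend on c

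**One arm, p4 = 50%, c = 40%.** The first-event value is 0.50 + 0.50 × 0.40 = 70%.

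| r | Status at 1 year | Overstatement | Patients per arm of 30 |
|---|---|---|---|
| 0% | 0.50 + 0.20 = 70% | 0 points | 0 |
| 10% | 0.45 + 0.20 = 65% | 5 points | 1.5 |
| 20% | 0.40 + 0.20 = 60% | 10 points | 3 |

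**Wider range.** For p4 from 40% to 80%, r = 10% gives 4 to 8 points (1.2 to 2.4 patients per arm). For the same p4, r = 30% gives 12 to 24 points (3.6 to 7.2 patients).

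**Between arms.** The first-event difference minus the status difference is p4·r in the interventional arm minus p4·r in the conservative arm. Take p4 = 70% v 50% and c = 40% in both arms. The first-event values are 0.70 + 0.30 × 0.40 = 82% and 70%, a difference of +12 points whatever r is.

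| r, interventional | r, conservative | Status at 1 year | Difference |
|---|---|---|---|
| 0% | 0% | 82% v 70% | +12 |
| 10% | 10% | 75% v 65% | +10 |
| 20% | 0% | 68% v 70% | −2 |
| 0% | 20% | 82% v 60% | +22 |

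The shift can go either way. For scale, the standard error of the difference in the third row is √[(0.68 × 0.32 + 0.70 × 0.30)/30] = √(0.4276/30) ≈ 0.119, about 12 points. A shift of 0.70 × 0.20 = 14 points is therefore similar in size to the sampling error.

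**The case against.** **Nothing says that absorbed collections refill.** This stands. The nearest text is the primary outcome, "New onset of wound CSF leakage or tension pseudomeningocele necessitating revision surgery", which shows that worsening is expected in some patients but does not concern collections already absorbed. A reader might infer that reversal is an established feature of this trial; the documents do not support that.

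**The event is not defined.** This also stands. Section 9 does not say that the first absorbed scan is final. The event could be sustained absorption, and event coding is commonly left to a statistical analysis plan, which is not shown here. What remains is that the protocol fixes a method that does not, on its usual reading, answer its own objective, and names no status comparison beside it.

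**The logistic regression could cover absorption.** It names neither an outcome nor a time, so it cannot be read as the missing comparison.

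**The log-rank test would be wrongly significant.** A reader might infer that re-accumulation raises its rejection rate. It does not: re-accumulation never enters a first-event test. A log-rank result favouring one arm alongside equal 1-year status would reflect a difference in first absorption, which is real as far as it goes. The error would lie in reading it as a result about status at 1 year.

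**Reach is limited.** Absorption is listed among the secondary objectives, and the chi-square comparison of revision surgery is unaffected. Against that, Section 8 bases the sample size on absorption.

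**Conclusion.** The point holds as a mismatch between objective and analysis. The protocol asks about absorption at 4 months and at 1 year, and Section 9 names no comparison at either time. Under standard first-event coding, the one method named estimates *ever absorbed* by 1 year.

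The size cannot be derived from the documents. The overstatement is p4 × r: 5 to 10 points in an arm with an assumed 50% absorbed at 4 months and 10% to 20% of those re-accumulating, and zero if none do. Where p4 × r is equal in the two arms, both 1-year levels are too high but their difference is right; the comparison is distorted only where the product differs. It would go too far to say that the trial will report refilled collections as absorbed, since that depends on event coding and re-accumulation rates that the documents do not give. The mismatch should be corrected, and it leaves the revision-surgery comparison untouched.

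**What to change.** In Section 9:
1. Add a comparison of the proportion absorbed at 4 months and of the proportion absorbed at 1 year, by randomised arm, using each scan's own status. Report a risk difference with its confidence interval at each time.
2. State one definition of absorbed and apply it to both scans. Count a collection that met it at 4 months but not at 1 year as not absorbed at 1 year.
3. Report the number re-accumulated by arm.
4. If the Kaplan-Meier and log-rank analysis is kept, label it time to first absorption and do not use it for the 1-year conclusion.

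The cost is one more analysis paragraph and less weight on a survival curve that, with two scans, would have essentially two steps. No new data are needed, because both scans are planned and size is measured at each.

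### Efficiency only: GOSE is compared with an unstratified Mann-Whitney test although randomisation is stratified by age and BMI, so a stratified rank test would be a near-free gain

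*Protocol*

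**What the plan says.** Section 2 lists GOSE as a secondary objective: "To assess functional recovery using the Glasgow Outcome Scale–Extended (GOSE) at 1 year post-surgery". Section 6 describes an ordinal score in which "GOSE scores range from 1 (death) to 8 (upper good recovery". It is measured once, at one year, and no baseline GOSE is mentioned.

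On allocation, Section 7 says: "Randomization will be stratified by age and body mass index". The cut-points are not given.

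On analysis, Section 9 says: "GOSE scores will be analyzed using a Mann-Whitney U test to assess differences in functional recovery between groups". No stratum or covariate is attached to that test. A separate item in Section 9 reads: "Multivariate logistic regression will be used to adjust for potential confounders, such as baseline health status, age, and type of initial surgery". It names no outcome, and its list of examples does not include BMI.

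Section 8 sizes the trial on absorption, not on GOSE: "30 per group) will be required to detect a clinically significant difference in pseudomeningocele absorption between the two groups". The power given there is 80%, at a significance level of 0.05.

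**The concern.** Stratified randomisation with blocking balances the strata across arms, so stratum differences in outcome largely cancel out of the treatment comparison. A test that ignores the strata still counts those differences as noise. If the strata are prognostic, its standard error is too large: it rejects less often than 5% under the null and has less power than it could have.

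Eligibility runs from 18 to 80 years, so some dependence of one-year function on age is plausible. With 30 patients per arm there is little power to spare. At stake is the sensitivity of the only functional-recovery comparison in the trial. Age and BMI must be known for every patient at randomisation, so using them needs no further data.

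**Working it through.** **Figures in the plan.** The protocol states no power for GOSE, so there is nothing to reproduce for this outcome. The 60 patients in Section 8 cannot be reproduced either, because no absorption rates or effect size are given. Neither affects the check below.

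**Inputs from the protocol.** 30 per arm, 1:1 allocation, stratification by age and BMI, GOSE on 8 levels, alpha 0.05 (taken as two-sided).

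**Assumptions, none of them in the protocol.** Two age groups by two BMI groups; permuted blocks of 4 within strata; GOSE skewed towards good recovery; a share R² of latent outcome variation explained by the strata, varied from 0 to 30%.

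**Step 1: type I error by approximation.** With strata balanced, the true variance of the arm difference is about (1 − R²) times the variance that the unadjusted test assumes. Hence

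actual alpha ≈ 2 × [1 − Φ(1.96 / √(1 − R²))]

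- R² = 0.10: 1.96 / 0.949 = 2.07, alpha ≈ 3.9%
- R² = 0.20: 1.96 / 0.894 = 2.19, alpha ≈ 2.8%
- R² = 0.30: 1.96 / 0.837 = 2.34, alpha ≈ 1.9%

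**Step 2: simulated type I error on the 8-level score.** Set A uses a normal latent scale with total variance held fixed (4,000 trials per scenario). Set B uses a log-odds scale.

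| R² | Mann-Whitney, set A | Mann-Whitney, set B | van Elteren, set A | rank-ANCOVA, set A |
|---|---|---|---|---|
| 0 | 5.3% | 4.6% | 5.3% | 5.4% |
| 0.10 | 4.1% | 3.8% | 4.9% | 5.2% |
| 0.20 | 2.9% | 2.8% | 4.9% | 5.2% |
| 0.30 | 2.5% | 1.7% | 5.2% | 5.4% |

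In set B the two adjusted tests were also at about 5%. Both sets agree with Step 1.

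**Step 3: simulated power at a large effect.** Set A uses a latent shift of 0.75 SD. Set B uses a log-odds of 1.4, an odds ratio of e^1.4 ≈ 4.1.

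| R² | A: Mann-Whitney | A: van Elteren / rank-ANCOVA | B: Mann-Whitney | B: adjusted tests |
|---|---|---|---|---|
| 0 | 72% | 71 / 71% | 77% | 76–77% |
| 0.10 | 71% | 73 / 74% | 72% | 75% |
| 0.20 | 71% | 76 / 76% | 67% | 74% |
| 0.30 | 72% | 81 / 81% | 56% | 70% |

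The loss is 2–3, 5 and 8–9 points in set A, and 75 − 72 = 3, 74 − 67 = 7 and 70 − 56 = 14 points in set B. The sets differ because A fixes the effect relative to total variation and B fixes it within strata. At R² = 0 the adjusted tests lose about 1 point or less. Simulation error is about 0.7 points per power figure in set A: √(0.7 × 0.3 / 4000).

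**Step 4: modest effects.** A further simulation assumed 65% of controls at level 8, R² of 0.10, 0.20 and 0.33, and an adjusted test that also used a health score.

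- Odds ratio 2: Mann-Whitney 21, 17 and 14%; adjusted 22, 20 and 19% (gain 1, 3 and 5 points).
- Odds ratio 1.5: Mann-Whitney 9, 9 and 8%; adjusted 10, 11 and 11% (gain 1, 2 and 3 points).
- Odds ratio 2 with only 40% at level 8: Mann-Whitney 25, 21 and 18%; adjusted 28, 27 and 26% (gain 3, 6 and 8 points).

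**The case against.** The strongest reply is that nothing here is wrong. Mann-Whitney is a standard, simple and robust test for an ordinal score in 60 patients. It does not inflate error, GOSE is secondary, and covariate adjustment is often settled in an SAP that is not at hand. Most of this stands, and it limits the point to efficiency. It does not remove the point, because the protocol names both the stratified design and the unstratified test, so the mismatch is in the text and not a gap left to a later document.

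The reply that the gains rest on favourable assumptions also stands in part. Nothing in the protocol supports a given R² or an odds ratio near 4, and no reason is given why BMI should predict GOSE. Elective patients without severe comorbidity may cluster near the top of the scale. At modest effects power is low under either test, so the change would seldom alter a conclusion.

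A further objection is that van Elteren cannot be specified until the strata are defined. That is true, but the randomisation needs those definitions anyway, and a rank-ANCOVA can use age and BMI as continuous values. It is also fair that a rank-ANCOVA coefficient is a difference in mean ranks and not a clinically readable GOSE effect. The gain claimed is in the test.

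A reader might infer three stronger points that the text does not support:

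- That baseline health status is already recorded and available. Section 9 only offers it as an example of what to "adjust for potential confounders, such as baseline health status, age, and type of initial surgery"; no measure or time of collection is defined. Power gains that depend on it should not be counted.
- That the logistic regression certainly excludes GOSE. It names no outcome, so it neither covers nor excludes GOSE. As written, a binary model does not fit an 8-level score unless GOSE is dichotomised or the model is ordinal, and the protocol says neither.
- That power is lost for no reason. Simplicity and independence from undefined covariates are reasons.

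**Conclusion.** The point holds as an efficiency improvement. The GOSE comparison as planned is valid, but conservative if age and BMI are prognostic. With the strata explaining an assumed 10% to 30% of outcome variation, the true type I error is roughly 2% to 4% instead of 5%, and about 2 to 14 points of power are lost at a large assumed effect. At odds ratios of 1.5 to 2 the gain was 1 to 8 points even with a health score added, and 1 to 5 points with the more skewed GOSE. If the strata are uninformative, the cost of stratifying is at most about 1 to 2 points.

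These figures rest on four strata, blocked allocation and a skewed GOSE, none of which the protocol states. The conservatism in particular needs balance within strata. It would not arise if allocation within strata were unblocked, although an adjusted test could still gain power.

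It would be wrong to conclude that the GOSE result would be biased or its error rate inflated, or that any stated power is undermined: the 60 patients are not sized on this outcome.

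**What to change.** In Section 9, make the GOSE test one of the following:

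- a van Elteren (stratified Wilcoxon) test over the age and BMI randomisation strata; or
- a rank-based ANCOVA that regresses the ranks of GOSE on arm, age and BMI.

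In either case rank death lowest, as GOSE 1, and keep the unadjusted Mann-Whitney test as a sensitivity analysis. Write down the age and BMI cut-points used for randomisation, so that the strata in the analysis match them. Add baseline health status only if a measure is defined and collected before randomisation. State which outcome the logistic regression serves.

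The cost is a wording change and a few lines of code, with no new patients and no new data for the age and BMI version. The statistical price is at most about 1 to 2 points of power if neither factor predicts GOSE. The choice should be fixed before outcome data are seen, so that it cannot depend on the results.

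### Randomisation is stratified by age and BMI, but the primary chi-square test uses neither factor and the adjusted model does not name BMI; the likely cost is some power, not bias

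*Protocol*

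**What the plan says.** Section 7 of the protocol states: "Randomization will be stratified by age and body mass index". It gives no cut-points for either factor.

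Section 9 fixes the primary comparison. The proportions needing revision surgery "will be compared between the two groups using a chi-square test", with no mention of strata or covariates. A separate paragraph adds: "Multivariate logistic regression will be used to adjust for potential confounders, such as baseline health status, age, and type of initial surgery". That sentence offers its covariates as examples, does not say which outcome is modelled and does not fix the coding of health status or surgery type.

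Section 8 gives 60 patients, 30 per group, "with a power of 80% and an alpha of 0.05". The size is set "to detect a clinically significant difference in pseudomeningocele absorption between the two groups", not for the primary outcome, and no event rate for the primary outcome appears anywhere in the protocol.

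Baseline grade on the Pseudomeningocele Palpation Scale (PPS) is an eligibility criterion in Section 4. It is not a stratification factor.

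**The concern.** Stratifying the randomisation forces balance on age and BMI. The gain in precision is realised only if the analysis uses those factors. An ordinary chi-square test estimates its variance as though allocation had been unrestricted, so variation between strata stays in the standard error although the design has removed it from the treatment comparison. The protocol has settled the test and named covariates, and neither the test nor the named list matches its own randomisation: BMI, one of only two factors chosen for stratification, is used nowhere.

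The adjusted model, as the only place where any covariate enters, raises a second question. With 60 patients and a binary outcome it may have too few events for the terms it names, in which case the adjusted result could be unstable or could depend on which terms are dropped to make it converge.

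**Working it through.** **The plan's own figure.** The 60 patients cannot be confirmed or refuted, because Section 8 gives no rates, effect size or sidedness. Worked backwards with the two-sided formula without continuity correction, n per arm = [1.96·√(2p̄q̄) + 0.84·√(p₁q₁ + p₂q₂)]² / (p₁ − p₂)², 30 per arm fits for example 10% vs 41% or 30% vs 66%. For a continuous measure it fits a standardised difference of about 0.73. None of this yields a primary event rate, so the steps below use assumed rates.

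**Step 1: cost of ignoring the strata.** Assumptions: 30 per arm, two age and two BMI levels (four equal strata), permuted blocks of 4, 20,000 simulated trials per setting, 5% two-sided. The chi-square statistic is d² / [p(1−p)(1/n₁ + 1/n₀)]. The Cochran-Mantel-Haenszel (CMH) statistic is [Σ(xₛ − n₁ₛmₛ/Nₛ)]² / Σ[n₁ₛn₀ₛmₛ(Nₛ−mₛ) / (Nₛ²(Nₛ−1))]. Both are compared with 3.84. Power is for a treatment odds ratio of 0.25.

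| Reference-stratum risk | Odds ratio for each factor | Type I: chi-square vs CMH | Power: chi-square vs CMH |
|---|---|---|---|
| 10% | 1 | 0.050 vs 0.047 | 0.171 vs 0.164 |
| 10% | 3 | 0.037 vs 0.048 | 0.443 vs 0.468 |
| 20% | 3 | 0.040 vs 0.051 | 0.580 vs 0.623 |
| 10% | 5 | 0.027 vs 0.049 | 0.468 vs 0.547 |

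Power lost with prognostic strata: 2.5, 4.3 and 7.9 points.

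A hand check of the second row. Odds of 1/9, 3/9, 3/9 and 9/9 give stratum risks of 10%, 25%, 25% and 50%, mean 27.5%.

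- Variance the chi-square uses: 0.275 × 0.725 = 0.199.
- Mean within-stratum variance: (0.090 + 0.1875 + 0.1875 + 0.250)/4 = 0.179.
- Ratio 0.897, so the effective critical value is 1.96/√0.897 = 2.07, a two-sided error of 0.038 (simulated 0.037).

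The same steps for the last row give a mean risk of 38.7%, a ratio of 0.784, a critical value of 2.21 and an error of 0.027, as simulated. For the third row the mean risk is 43.7%. The losses of 2 to 8 points therefore belong to control-arm rates of about 28% to 44%, as well as to strong assumed stratum effects.

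**Step 2: how many terms 60 patients can carry.** Treatment plus the three named covariates at one degree of freedom each is four parameters. The smaller outcome class cannot exceed 30, so events per parameter are at most 30/4 = 7.5. Five per parameter needs 20 events, an overall rate of 20/60 = 33% (up to 67%, where non-events become the smaller class). The binomial chance of 20 or more events is below 0.0001 at a 10% rate, 0.011 at 20% and 0.33 at 30%.

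At assumed rates of 10%, 15% and 20% there are 6, 9 and 12 events: 1.5, 2.2 and 3.0 per parameter with four parameters. With a 3-level health status and a 4-level surgery type there are 1 + 1 + 2 + 3 = 7 parameters, giving 0.9, 1.3 and 1.7.

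**Step 3: separation under ordinary maximum likelihood** (600 to 2,000 simulated trials per setting, same event rate in both arms):

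| Model | 10% | 15% | 20% |
|---|---|---|---|
| Named covariates, health status and surgery type binary | 18–20% | 4–6% | 0.5–1% |
| Same, 3-level and 4-level, equal category sizes | 70–72% | 41% | 19–20% |
| Treatment, continuous age and continuous BMI only | 10.5% | 1% | 0.3% |

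With unequal categories (assumed 50/35/15% and 50/25/15/10%) the multi-level figures rise to 86%, 69% and 52%. At a 30% event rate they fall to 4% with equal multi-level coding and 0.1% with binary coding.

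**The case against.** The strongest reply is that nothing here invalidates the primary test. That stands. A reader might infer that ignoring the strata biases the comparison or raises the false-positive rate; Step 1 shows the opposite direction, and no difference that matters if age and BMI are not prognostic. The protocol does not say that they are.

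The covariate list is open, and a statistical analysis plan that is not shown may complete it. So BMI is not named, which is weaker than being excluded. What remains is that the protocol does fix the primary test, and that test uses neither factor.

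A reader might also take the absence of baseline PPS as an error. It contradicts nothing: PPS is an entry criterion, not a stratification factor. Grade IV describes a tense lesion, which is close to one component of the primary outcome, so it is a sensible optional covariate and no more.

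Finally, a reader might infer that the adjusted model will usually fail, from the 70% in Step 3. That figure needs a 10% event rate and a seven-parameter coding, and the protocol states neither. With binary factors at the same rate it is about 20%. Failure of that model would also leave the primary chi-square result intact. Calling for more covariates while warning of too few events would be inconsistent, which is why the primary model below is kept small.

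**Conclusion.** The mismatch between Sections 7 and 9 is real and worth correcting, but modest in effect. The unstratified chi-square is valid and, if the strata are prognostic, conservative: type I error about 0.03 to 0.04 and roughly 2 to 8 points of power lost, under assumed stratum odds ratios of 3 to 5, assumed 2×2 strata and fairly high event rates. With non-prognostic strata there is essentially nothing to gain or lose.

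The ceiling of 7.5 events for each of four parameters rests only on the 60 patients and a binary outcome. The rest of the sparse-events caution assumes that the adjusted model is for the primary outcome and that the overall rate is 10% to 20%. On that basis separation ranges from about 1% to 20% of trials with binary covariates and from about 20% to 70% with equal-sized multi-level categories. This supports a small penalised model, not a claim that the planned one cannot be fitted.

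**What to change.** Amend Section 9 as follows.

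- Primary analysis: a Cochran-Mantel-Haenszel test with a Mantel-Haenszel risk difference over the age and BMI strata used for randomisation. State in advance that if strata are sparse, Firth-penalised logistic regression with treatment, age and BMI replaces it, and define sparse.
- Keep the plain chi-square test as a supportive analysis.
- Name the outcome of the model with health status and type of initial surgery, fix the coding of both, and make it a sensitivity analysis fitted with a penalised method.
- Baseline PPS grade may be added as an optional covariate.

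Cost: slightly more analysis work and no new data, since age, BMI and PPS are already needed for randomisation or eligibility. The age and BMI cut-points used in the randomisation, which the protocol does not state, must be recorded and carried into the analysis.
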